3.7.1.1 Adverse Events of Special Interest

The following Adverse Events of Special Interest (AESI) will be summarized; the infusion related reaction, anaphylactic reaction and hypersensitivity will be collected from the case report form. Infections will be identified by the corresponding System Organ Class (SOC); for remaining AESIs, relevant search criteria will be established prior to database lock.

- Infusion Related Reaction
- Anaphylactic Reaction
- Hypersensitivity
- Infections
- Hepatic Function Abnormality
- Cytopenia
- Opportunistic Infection
- Progressive Multifocal Leukoencephalopathy (PML)

Symptoms corresponding to infusion-related reaction will be summarized separately and will not be combined with TEAE analysis.

3.7.1.2 Deaths and Treatment Discontinuations due to Adverse Events

Deaths, fatal AEs, and AEs leading to discontinuation of IP will be summarized.

3.7.2 Analysis of Adverse Events and Serious Adverse Events

Treatment-Emergent adverse events and serious adverse events during RCP, OLP, SFP and any MEDI-551 exposure will be summarized as described in Table 3.7.2.2-1.

TEAEs per 100 Person-years for a specific reporting period will be calculated as

$$= 100 \times \frac{\text{Total number of TEAEs for specific reporting period}}{\text{Total Person years for specific reporting period}}$$

See Table 3.3.3-1 for definition of person-years.

3.7.2.1 Analysis of non-NMO related TEAE

Number (%) of cases will be summarized by preferred term for RCP to establish the degree of agreement between the Adjudication Committee and the investigator's decision about

symptoms not being related to NMO and thus reported as TEAEs. The denominator will be decided by the total number of each such symptom reported.

3.7.2.2 Subgroup Analyses of Adverse Events

Treatment-Emergent adverse events (by SOC and PT) during RCP will be summarized by sex (male vs female).

Table 3.7.2.2-1 Type of TEAE Analysis by Period

Type of TEAE Analysis	RCP	OLP	SFP	Any MEDI-551 Exposure
Overall Summary of TEAEs	X	X	X	X
TEAEs by SOC and PT	X	X	X	X
IP Related TEAEs by SOC, PT	X	X		X
TEAEs with severity ≥ Grade 3 by SOC and PT	X	X		X
TESAEs by SOC and PT	X	X	X	X
TEASEs by Seriousness Criteria	X	X	X	X
TEAEs resulting in permanent discontinuation of the IP by SOC and PT	X	X		X
TEAEs resulting in death by SOC and PT	X	X	X	X
TEAEs (≥5% in MEDI-551)	X	X		X
TEAEs by SOC, PT and by Highest Severity	X	X	X	X
IP Related TEAEs by SOC, PT and by Highest Severity	X	X		X
IP Related TEAEs with Severity ≥ Grade 3 by SOC and PT	X	X		X
IP Related TESAEs by SOC and PT	X	X		X
TEAEs with Severity ≥ Grade 3 and/or TESAEs by SOC and PT	X	X		X
IP Related TEAEs with Severity ≥ Grade 3 and/or TESAEs by SOC and PT	X	X		X
TEAEs by PT sorted by frequency in MEDI-551 group	X	X		X
TEASEs by Preferred Term Sorted by Frequency	X	X	X	X
All deaths	X	X	X	X
AESI by SOC and PT	X	X	X	X
TEAEs per 100 Person-years	X	X		X
TESAEs per 100 Person-years	X	X		X
‘X’ represents that an analysis will be performed for this period				

3.7.3 Clinical Laboratory Evaluation

Laboratory parameters will be assessed at baseline as well as throughout the study. Laboratory toxicities will be defined based on the National Cancer Institute's Common Terminology Criteria for Adverse Events Version 4.0 (NCI CTCAE V 4.0).

Following analyses will be presented for RCP and OLP:

- Grade 3-4 Clinical Laboratory Toxicities
- Baseline Toxicity Grade in different Laboratory Categories
- Worst Toxicity Grade (during post-baseline period) in different Laboratory Categories
- Toxicity Grade by Visit in different Laboratory Categories
- At Least 2-Grade Shift from Baseline to Worst Toxicity Grade in different Laboratory Categories
- Shifts from Baseline Relative to the Normal Range in different Laboratory Categories
- Absolute values, change and percent changes in Laboratory values

3.7.4 Other Safety Evaluations

3.7.4.1 Columbia Suicide Severity Rating Scale

The C-SSRS involves a series of probing questions that inquire about possible suicidal thinking and behavior, and classifies these events of interest into 11 categories of interest as part of the assessment process. The terminology considered important includes 5 levels of suicidal ideation, 5 levels of suicidal behavior, and the category "self-injurious behavior, no suicidal intent." Different versions of the C-SSRS are administered at different visits during the study. The "Baseline/Screening" questionnaire will be administered to each subject at screening. This version of the scale combines the "Baseline" and "Screening" versions to assess suicidality in a subject's lifetime and during a predefined time period. The "Since Last Visit" version of the C-SSRS will be administered at all visits for all subjects randomized into the study.

The following outcomes are C-SSRS categories and have binary responses (yes/no). The categories have been re-ordered from the actual scale to facilitate the definitions of the composite and comparative endpoints, and to enable clarity in the presentation of the results.

Table 3.7.4.1-1 C-SSRS categories for reporting	
Category #	Category
1	Wish to be Dead
2	Non-specific Active Suicidal Thoughts
3	Active Suicidal Ideation with Any Methods (Not Plan) without Intent to Act
4	Active Suicidal Ideation with Some Intent to Act, without Specific Plan
5	Active Suicidal Ideation with Specific Plan and Intent
6	Preparatory Acts or Behavior
7	Aborted Attempt
8	Interrupted Attempt
9	Actual Attempt (non-fatal)
10	Completed Suicide
11	Self-injurious behavior without suicidal intent (not suicide-related)

The following outcome is a numerical score derived from the C-SSRS categories. The score is created at each assessment for each subject and is used for determining treatment emergence.

Suicidal Ideation Score: The maximum suicidal ideation category (1-5 on the C-SSRS) present at the assessment. Assign a score of 0 if no ideation is present.

Composite endpoints to be evaluated based on the above categories are defined in Table 3.7.4.1-2. Some of these endpoints will depend on the definition of Suicidal Ideation Score defined below.

Table 3.7.4.1-2 Composite Endpoints based on C-SSRS	
Endpoint	Description
Suicidal ideation	A “yes” answer at any time during treatment to any 1 of the 5 suicidal ideation questions (Categories 1-5) on the C-SSRS.
Suicidal behaviour	A “yes” answer at any time during treatment to any 1 of the 5 suicidal behaviour questions (Categories 6-10) on the C-SSRS.
Suicidal ideation or behaviour	A “yes” answer at any time during treatment to any 1 of the 10 suicidal ideation and behaviour questions (Categories 1-10) on the C-SSRS.

Comparative endpoints to be evaluated are defined in Table 3.7.4.1-3.

Table 3.7.4.1-3 Comparative Endpoints based on C-SSRS	
Endpoint	Description
Treatment-emergent suicidal ideation compared to Baseline	An increase in the maximum suicidal ideation score during treatment from the maximum suicidal ideation category at baseline (excluding “lifetime” scores from the Baseline/Screening C-SSRS scale).
Treatment-emergent serious suicidal ideation compared to Baseline	An increase in the maximum suicidal ideation score to 4 or 5 on the C-SSRS during treatment from a baseline score of 0-3 (excluding “lifetime” scores from the Baseline/Screening C-SSRS scale).
Improvement in suicidal ideation	Defined as a decrease in suicidal ideation score at the time point of interest (eg, during RCP and OLP) from baseline.
Emergence of suicidal behaviour compared to all prior history	The occurrence of suicidal behaviour (Categories 6-10) during treatment from not having suicidal behaviour (Categories 6-10) at baseline (includes “lifetime” and/or “screening” scores from the Baseline/Screening C-SSRS scale).

Analysis of C-SSRS will be restricted to subjects who have at least one response at both baseline and post-baseline visits. Number (%) of subjects meeting each of the categories defined in Table 3.7.4.1-2 and Table 3.7.4.1-3 and suicidal ideation score will be presented descriptively; no p-value will be produced. Missing data will not be imputed.

3.7.4.2 Vital Signs

Change from Baseline in the following vital sign parameters will be collected in this study: systolic blood pressure, diastolic blood pressure, body temperature, pulse rate, and respiratory rate.

Vital signs data will be summarized by visit and by treatment group using descriptive statistics. For vital sign assessments collected on the dosing day, the vital sign data will be presented by time points of interest as well. The time points of interest are as follows:

- Pre-dose assessment;
- During dose assessment: 15min, 30min;
- After dose assessment: immediately after dosing, the last assessment before discharge.

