3.1.3 Management of Study Medication Related Toxicities

Infusion-related reaction is the only identified risk of IV MEDI-551 to date and has occurred in both MEDI-551 oncology and non-oncology studies. For subjects experiencing an infusion-related reaction, an approach to these reactions based on severity of symptoms is presented in Table 3 and Appendix 2 (National Institute of Allergy and Infectious Diseases [NIAID] and Food Allergy and Anaphylaxis Network [FAAN] Guidance for Anaphylaxis Diagnosis), with suggested treatment options. Final treatment is at the discretion of the investigator and should reflect local standard of care.

Table 3 An Approach to Management of Anaphylactic, Hypersensitivity, and Infusion Reactions

Severity of Symptoms	Treatment	Investigational Product

Mild reactions (infusion and hypersensitivity) Mild infusion reactions such as headache, nausea, nonpruritic rash, or mild hypersensitivity reactions including localized cutaneous reactions such as mild pruritus, flushing, rash, dizziness, headache, ≤ 20 mmHg change in systolic BP from pre-infusion measurement
	
 • Evaluate subject, including close monitoring of vital signs • At the discretion of the investigator, treat subject, for example, with: 
 • Normal saline (~500-1000 mL/hour IV) and/or • Diphenhydramine 50 mg IV or equivalent and/or • Acetaminophen 500-650 mg or equivalent dose of paracetamol and/or • Topical antihistamines and/or low-potency topical corticosteroid preparations and/or • Anti-nausea medication, as needed 	
 • Stop IP infusion immediately • Once the event has resolved, resume current IP infusion under observation and complete IP infusion at no more than half the planned infusion rate

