- 1 Women of childbearing potential must have a negative urine pregnancy test prior to receiving MEDI-551 or placebo
- 2 Subjects with signs or symptoms of clinically significant infections at the time of planned infusion of MEDI-551 or placebo should not be retreated until the infection has resolved.
- 3 MEDI-551 or placebo must be administered at room temperature by controlled infusion via an infusion pump into a peripheral vein at a rate of 42 mL/hr for the first 30 minutes, with the rate escalated in accordance with Table 16, unless an infusion reaction occurs necessitating the modulation or stopping of the infusion.
- 4 MEDI-551 or placebo must not be administered via IV push or bolus but as a slow IV infusion. The entire content of the IV bag will be infused using an infusion pump using a 0.22 or 0.2 micron filter.

Table 16 Infusion Times for IV Administration of MEDI-551 300 mg or Placebo

Number of IV Bags	Cumulative Time (minutes)	Infusion Rate (mL/hour)	Infusion Rate (mg/hour)	Total mg Infused
1	0-30	42	50	25
	31-60	125	150	75
	61-90	333	400	200

IV = intravenous

- 5 A physician must be present at the site or immediately available to respond to emergencies during all administrations of MEDI-551 or placebo. Fully functional resuscitation facilities should be available.
- 6 At Day 1 and Day 15 of the RCP and OLP Day 1 and OLP Day 15 and at subsequent dosing visits in the OLP, all study subjects will be premedicated with IV methylprednisolone (80-125 mg or equivalent glucocorticoid), PO acetaminophen (500-650 mg) or equivalent dose of paracetamol, and PO diphenhydramine (25-50 mg) or equivalent antihistamine, 30 to 60 minutes prior to MEDI-551 or placebo administration to mitigate infusion reactions.
- 7 Prior to the start of the infusion, please be sure that the bag content is at room temperature to avoid an infusion reaction due to the administration of the solution at low temperatures.
- 8 Because of the possible need to vary infusion rates depending on tolerance of the infusion, the total infusion time may exceed the time stated in Table 16. **UNLESS AN INFUSION REACTION OCCURS RESULTING IN DISCONTINUATION, THE ENTIRE INFUSION BAG CONTENTS MUST BE ADMINISTERED.**
- 9 If there are no requirements to slow, interrupt or permanently stop the infusion, the anticipated infusion time to deliver each dose is anticipated to be 90 minutes ± 15 minutes.

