4.5.1.3 Monitoring of Dose Administration

Vital signs (body temperature, BP, pulse rate, and respiratory rate) must be taken with the subject in a semi-supine position as follows:

- Within 60 minutes prior to investigational product administration
- Every 15 minutes (\pm 5 minutes) during the infusion
- Immediately (\pm 5 minutes) after the end of the infusion
- Every 30 minutes (\pm 5 minutes) for 2 hours after dosing or until stable, whichever is later

If a hypersensitivity reaction occurs during the infusion, vital signs will be taken more frequently, as warranted by the severity of the reaction.

As with any antibody, allergic reactions to dose administration are possible. Therefore, appropriate drugs and medical equipment to treat acute anaphylactic reactions must be immediately available, and study personnel must be trained to recognize and treat anaphylaxis.

For Japanese subjects only, the initial dose on Day 1 of the RCP should be administered as a patient in-hospital procedure. The subject can be discharged the next day (Day 2) if no abnormal findings are observed.

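### The SAP's by-arm summary of vital signs during infusion stops at 30 minutes, within the lowest-rate step, so a transient change between then and the end of infusion would not show in any time-point summary

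*SAP*

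**What the plan says.** SAP 3.7.4.2 begins with a general rule: "Vital signs data will be summarized by visit and by treatment group using descriptive statistics". For dosing days it adds a list of time points of interest: a pre-dose reading, then "During dose assessment: 15min, 30min", then "After dose assessment: immediately after dosing, the last assessment before discharge". The SAP's amendment history dates this list to 31 October 2016. No reason is given for ending the on-infusion points at 30 minutes.

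The protocol collects more than this. Section 4.5.1.3 (and likewise 4.3.3.5) asks for a reading in the hour before dosing, then "Every 15 minutes (\pm 5 minutes) during the infusion", then one at the end of the infusion, then half-hourly readings "for 2 hours after dosing or until stable, whichever is later".

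The infusion itself is set out in Protocol 4.5.1.2, Table 16 ("Infusion Times for IV Administration of MEDI-551 300 mg or Placebo"). It has three 30-minute steps at rising rates, and the planned total is 90 minutes, give or take 15.

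**The concern.** The two on-infusion points chosen for the by-arm summary both precede the first rate increase. The part of the infusion in which the rate rises and most of the dose is delivered is represented only by the reading taken once it is over.

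This matters because Protocol 3.1.3 states: "Infusion-related reaction is the only identified risk of IV MEDI-551 to date". Vital signs are the one scheduled, objective measurement of that risk taken in every dosed subject in both arms. A fall in blood pressure or rise in pulse that appears at 45 to 75 minutes and has settled by the end of infusion would contribute to none of the named time points. The by-visit summary does not clearly fill the gap, since the SAP does not say which of the many dosing-day readings represents the visit.

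**Working it through.** **Inputs.** Protocol Table 16: 42 mL/h for 0–30 min (25 mg), 125 mL/h for 31–60 min (75 mg), 333 mL/h for 61–90 min (200 mg). Protocol 4.5.1.1: one 250 mL bag per dose, so 300 mg / 250 mL = 1.2 mg/mL. Reading times: Protocol 4.5.1.3. Summarised points: SAP 3.7.4.2.

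**Step 1: reproduce Table 16.** mg per step = rate (mL/h) × 0.5 h × 1.2 mg/mL.

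- 0–30 min: 42 × 0.5 × 1.2 = 25.2 mg (table: 25)
- 31–60 min: 125 × 0.5 × 1.2 = 75.0 mg (table: 75)
- 61–90 min: 333 × 0.5 × 1.2 = 199.8 mg (table: 200)

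The volumes sum to 21 + 62.5 + 166.5 = 250 mL and the amounts to 300 mg, so the table is internally consistent.

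**Step 2: share of dose before and after minute 30.** By 30 min: 25 / 300 = 8.3%. Afterwards: (75 + 200) / 300 = 91.7%. Using the table's mg/h column, the later rates are 150 / 50 = 3 and 400 / 50 = 8 times the first.

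**Step 3: cumulative dose at each scheduled reading**, from 50, 150 and 400 mg/h in turn, assuming no slowing or interruption.

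| Reading | Cumulative mg | % of 300 mg | In the SAP time-point list? |
|---|---|---|---|
| 15 min | 50 × 0.25 = 12.5 | 4.2 | yes |
| 30 min | 50 × 0.5 = 25 | 8.3 | yes |
| 45 min | 25 + 150 × 0.25 = 62.5 | 20.8 | no |
| 60 min | 25 + 75 = 100 | 33.3 | no |
| 75 min | 100 + 400 × 0.25 = 200 | 66.7 | no |
| 90 min / end | 300 | 100 | yes, as the reading immediately after dosing |

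The 45 and 60 minute readings follow the first rate increase; the 75 minute reading follows the second.

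**Step 4: the collection window.** The ±5 minute tolerance changes little. A 30 minute reading taken at 35 minutes corresponds to 25 + 150 × 5/60 = 37.5 mg, or 12.5% of the dose.

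**The case against.** The strongest reply is that this is one supplementary descriptive table and that the safety question is mainly answered elsewhere. Much of that stands.

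- SAP 3.1 puts all data into listings, so the later readings are neither lost nor unavailable. A reader might infer that the SAP throws them away; it does not. Listings, however, do not compare the arms.
- The end-of-infusion reading is summarised. It follows the fastest step directly and would show any change that persists. What it cannot show is a change that has already resolved.
- Protocol 4.3.3.5 has abnormal vital signs reported as adverse events or as signs and symptoms of the disease. SAP 3.7.1.1 summarises infusion-related reaction, anaphylactic reaction and hypersensitivity as events of special interest, and an unmasked monitoring committee reviews safety regularly. These are the main outputs for the risk. They rest on investigator reports, so a summary of the measured values complements them.
- The systolic cut-points in Protocol Table 3 are single elements of multi-symptom management grades, and the protocol does not commit to tabulating them. That is correct, and counts against them can only be optional.
- Clock time matches the rate step only if the infusion runs as planned. In a subject who reacts, the infusion is stopped and resumed more slowly, so fixed 45, 60 and 75 minute columns would be misaligned for the subjects of most interest. This is a fair criticism of a fixed-time table used alone, and it is why a maximum-change summary is also needed.

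**Conclusion.** The point holds as a limited gap in descriptive safety reporting. The by-arm on-infusion summary covers readings up to 8.3% of the dose at the lowest rate, and three scheduled readings (about 45, 60 and 75 minutes) appear in no time-point summary. What could go unseen there is a transient change between about 30 minutes and the end of infusion. The dose figures assume an uninterrupted infusion. No hypothesis test, error rate or efficacy estimate is touched, and the protocol and SAP do not contradict each other, because the protocol promises only a descriptive summary of vital signs.

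Two stronger readings are tempting and are not supported. A reader might infer that systolic change from pre-infusion, which Protocol Table 3 uses in describing severity, cannot be described at all. It can be, at 15 minutes, 30 minutes, immediately after dosing and the last reading before discharge, since pre-dose is on the list; only the maximum change over the infusion cannot be derived from those points. A reader might also count three of the four half-hourly post-dose readings as unused. That assumes the last reading before discharge is the 120 minute one. Monitoring can run beyond 2 hours until the subject is stable, and Japanese subjects receive the first dose in hospital with discharge possible the next day, so the last reading may be none of the four.

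**What to change.** In SAP 3.7.4.2:

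1. Extend the during-dose time points to every scheduled on-infusion reading, that is, add 45, 60 and 75 minutes to 15 and 30.
2. Add, by arm and separately for Day 1 and Day 15 of the randomized-controlled period, each subject's maximum on-infusion change from pre-dose (largest rise and largest fall) for each vital sign, taken over all readings from start to end of infusion. This does not depend on clock time and so also covers slowed or interrupted infusions. Show the number of on-infusion readings per subject beside it, because a longer infusion yields more readings and so a larger expected maximum.
3. Optionally, give the number and percentage of subjects with a systolic change above 20 mmHg and of at least 40 mmHg. These values are borrowed from Protocol Table 3 for reporting only.

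The cost is a few lines of SAP text, some programming and a longer descriptive table. Nothing changes in data collection, the infusion schedule or subject management.

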3.7.4.3 Electrocardiogram

Descriptive statistics for the following electrocardiogram (ECG) variables will be presented:

- Heart Rate (bpm), RR interval (msec), PR Interval (msec), Atrial rate (bpm), QRS duration (msec), Ventricular rate (bpm), QT interval (msec)

Corrected QT interval based on Fridericia approach, $QTc = QT/RR^{0.33}$ with QT in msec and RR in seconds will also be derived and summarized descriptively. Furthermore, following summaries will be provided:

Number (%) of subjects meeting the following criteria:

- QTc interval > 450
- QTc interval > 480
- QTc interval > 500
- QTc interval increases from baseline > 30
- QTc interval increases from baseline > 60
- Result [Normal, Abnormal, not clinically significant, Abnormal, clinically significant], as collected on case report form.

3.7.4.4 Body Weight

Change from baseline in body weight will be summarized descriptively for RCP. Shift analysis of following BMI categories will be performed:

- Underweight (<18.5 kg/m²)
- Normal weight (18.5 kg/m² – 24.9 kg/m²)
- Overweight (25 kg/m² – 29.9 kg/m²)
- Obese (≥ 30 kg/m²)

3.8 Immunogenicity

Number (%) of subjects meeting the following will be summarized related to Anti-Drug Antibody (ADA):

- ADA positive at baseline
- ADA positive any time during post-baseline
- ADA positive at both baseline and any time post-baseline
- ADA positive at any time post-baseline but not detected (or missing) at baseline
- ADA not detected at any time post-baseline and detected at baseline
- Persistent positive (defined as positive at ≥ 2 post-baseline assessments (with ≥ 16 weeks between first and last positive) or positive at last post-baseline assessment)

- Transient positive (defined as negative at last post-baseline assessment and positive at only one post-baseline assessment or at ≥ 2 post-baseline assessments (with < 16 weeks between first and last positive))
- ADA positive during post-baseline by visit

Following additional analyses will be performed to assess the impact of ADA on efficacy:

Number (%) of subjects with an adjudicated NMO/NMOSD attack during RCP

- based on baseline ADA positive subjects
- by ADA status (positive or negative) where the status is considered in a cumulative manner at each time point (i.e., if a subject had a positive sample at any prior time before an efficacy assessment visit then that subject would be counted as positive through that time point)

Number (%) of subjects TEAEs (by SOC and PT) during RCP by ADA status will be summarized.

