4.3.8 Immunogenicity Evaluation and Methods

Serum samples for ADA will be collected from all subjects according to the schedules of procedures in Table 6, Table 7, Table 8, and Table 10.

Samples will be measured for the presence of ADA by MedImmune using a validated, drug-tolerant solution phase bridging assay. Tiered analyses will be performed to include screening, confirmatory, and titer assay components and positive-negative cut points will be employed that were statistically determined from drug naive validation. Evaluations will be performed at baseline prior to administration of investigational product and at routine time points during the treatment and follow-up phase of the study or at discontinuation.

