6.3 Study Timetable and End of Study

The end of the study ("study completion") is defined as the date of the last protocol-specified visit/assessment (including telephone contact) for the last subject in the study. This will occur when the last subject completes the 52-week SFP.

An individual subject will be considered to have completed the RCP if the subject was followed through Day 197 or experienced an NMO/NMOSD attack as determined by the AC, regardless of the number of doses the subject received. Additionally, all subjects enrolled in the RCP at time that the 67th AC-determined attack is confirmed, or at the time the Sponsor discontinues enrollment upon recommendation of the independent DMC based on evidence of efficacy and safety, will also be considered as completers, regardless of the number of doses the subject received, provided the subject completes the Day 197/EDV visit. A subject will be considered to have completed the OLP if the subject participated for the duration of the OLP as per Section 3.1.1.4. A subject will be considered to have completed the SFP if the subject was followed for 52 weeks (12 months) after the last dose of investigational product. Subjects will be considered not to have completed a study period if consent was withdrawn, death occurred, or the subject was lost to follow up.

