Appendix 1 Sample Size Calculation

The proposed study is being planned to detect a target relative reduction of 60% in risk for time (days) from Day 1 to onset of an AC-determined NMO/NMOSD attack on or before Day 197 with 90% power and $\alpha = 0.05$ (two-sided), assuming an unequal randomization ratio of 3:1 to MEDI-551 versus placebo. Using the following formula, a total of 67 AC-determined NMO/NMOSD attacks will be required:

$$E = \left[\frac{z_{1-\alpha/2} + z_{1-\beta}}{\ln(HR)} \right]^2 \times \frac{(r+1)^2}{r},$$

where $z_{1-\alpha/2}$ and $z_{1-\beta}$ are $100(1 - \alpha/2)^{\text{th}}$ and $100(1 - \beta)^{\text{th}}$ percentile of a standard normal distribution, $r = 3$ is the randomization ratio and $HR = \text{hazard ratio} = 0.4$.

Following the completion of the first 78 subjects in this study the sample size was reviewed. The attack rate of the first 78 subjects to complete the RCP was used to simulate the remaining subjects to estimate the probability of reaching the required 67 AC-determined attacks. The simulation showed that with a sample size of 252 subjects there is a 90% probability of reaching the required 67 AC-determined attacks.

The remaining text in this appendix describes the process of defining the original sample size of 212 subjects.

Assuming hazard rates of 1.5/year and 1.0/year for an NMO/NMOSD attack in the placebo arm for seropositive and seronegative groups, respectively, and using the following formula:

$$N = \frac{E}{\Pr(\text{Fail})},$$

a total of 212 (with an upward adjustment) subjects are expected to be enrolled in this study where

$$\Pr(\text{Fail}) = s_1 P_1 + s_2 P_2$$

is the weighted average of the failure probabilities P_1 and P_2 in seropositive and seronegative cohorts, respectively, with associated stratum specific weights $s_1 = 0.8$ and $s_2 = 0.2$. Recall that subjects will be enrolled to seropositive and seronegative cohorts in 80:20 ratio.

Furthermore, the probability of an attack within i^{th} cohort ($i = 1, 2$) is given by

$$P_i = (1 - w)p_{i0} + wp_{i1}$$

the weighted average of the failure probabilities p_{i0} and p_{i1} for placebo and MEDI-551 groups, respectively; $p_{i0} = 1 - e^{-\lambda_{i0}F}$, $p_{i1} = 1 - e^{-\lambda_{i1}F}$; $F = 197/365 = 0.54$ to indicate the 197 days (28 weeks) duration of the controlled portion of the study; note that based on the

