assumptions for this study, $\lambda_{10} = 1.5$, $\lambda_{11} = 0.6$, $\lambda_{20} = 1$ and $\lambda_{21} = 0.4$ and $w = \frac{r}{1+r} = 0.75$. Since the primary endpoint will be tested using the Cox proportional model, a simulation approach was used to investigate the power under alternative hypotheses mentioned above. Based on 5,000 simulations, the power for the overall and seropositive populations were observed as 94% and 91%, respectively. Moreover, the total required 67 events (212 subjects) were, on an average, distributed in seropositive and seronegative cohorts as 57 (168 subjects) and 10 (44 subjects) respectively.

The underlying hazard rate of time to an NMO/NMOSD attack in the seropositive placebo group is estimated based on a meta-analytic approach from several open-label cohort studies (see Table 7-1) in the absence of any placebo-controlled study in this population to date. These studies consisted of both seropositive and seronegative subjects and hence any finding related to hazard rate derived from these studies can be considered as an underestimation when applied for seropositive subgroup in the current study. Following are the 5 open-label studies considered with a total of 161 subjects:

Author	Title
Bedi et al	Impact of rituximab on relapse rate and disability in neuromyelitis optica. Mult Scler. 2011 Oct;17(10):1225-30
Costanzi et al	Costanzi C, Matiello M, Lucchinetti CF, Weinshenker BG, Pittock SJ, Mandrekar J, et al. Azathioprine: tolerability, efficacy, and predictors of benefit in neuromyelitis optica. Neurology. August 16, 2011;77(7):659-66.
Jacob et al	Treatment of neuromyelitis optica with rituximab: retrospective analysis of 25 patients. Muscle Nerve. 2008 Jan;39(1):87-90
Kim et al	Kim SH, Kim W, Li XF, Jung IJ, Kim HJ. Repeated treatment with rituximab based on the assessment of peripheral circulating memory B cells in patients with relapsing neuromyelitis optica over 2 years. Arch Neurol. 2011 Nov;68(11):1412-20.
Pittock et al	Pittock SJ, Lennon VA, McKeon A, Mandrekar J, Weinshenker BG, Lucchinetti CF, O'Toole O, Wingerchuk DM. Eculizumab in AQP4-IgG-positive relapsing neuromyelitis optica spectrum disorders: an open-label pilot study. Lancet Neurol. 2013 Jun;12(6):554-62.

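### A whole-RCP attack percentage split by cumulative ADA status tends to make ADA look harmless or protective, because an attack ends the chance of turning positive

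*SAP*

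**What the plan says.** SAP 3.8 introduces the tables with "Following additional analyses will be performed to assess the impact of ADA on efficacy". The statistic is "Number (%) of subjects with an adjudicated NMO/NMOSD attack during RCP", given once for subjects positive at baseline and once by ADA status. The second table carries the condition "where the status is considered in a cumulative manner at each time point". The SAP spells out what this means for a single subject: "if a subject had a positive sample at any prior time before an efficacy assessment visit then that subject would be counted as positive". No at-risk denominator, person-time, landmark or time-dependent model is given, and there is no rule for where a subject who moves from negative to positive is counted.

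On sampling, Protocol 4.3.8 says "Serum samples for ADA will be collected from all subjects according to the schedules of procedures in Table 6" and in the later schedules. In the RCP, Table 6 places samples at Days 1, 29, 85 and 197; Table 8 adds one at the Assessment Visit. On follow-up, Protocol 6.3 says "An individual subject will be considered to have completed the RCP if the subject was followed through Day 197 or experienced an NMO/NMOSD attack". The attack in question must be one that the Adjudication Committee has confirmed. Protocol 4.8.6.1 says only that the association of ADA with attack rate, among other things, may be evaluated.

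**The concern.** The outcome is a proportion over the whole RCP, but the grouping is a status that develops during the RCP and can be acquired only by subjects who have not yet had an attack. A subject whose attack comes before Day 29 can only be ADA negative unless already positive on Day 1. A subject who stays attack-free has further samples on which to turn positive. Newly positive subjects thus carry a guaranteed attack-free stretch, and the early attacks all fall in the negative group.

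The distortion runs in the reassuring direction. If ADA did reduce the effect of MEDI-551, this table could understate it; if ADA did nothing, the table could suggest that positive subjects do better. Immunogenicity is a secondary objective, so the table is likely to be read, even though no formal conclusion depends on it.

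**Working it through.** **1. Inputs from the documents.** MEDI-551 attack hazards of 0.6/year (seropositive) and 0.4/year (seronegative), mixed 80:20, over 197 days (SAP Appendix 1). ADA samples on Days 1, 29, 85 and 197 (Protocol Table 6). MEDI-551 subjects: 0.75 × 252 = 189.

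**2. Check of the design inputs.** The plan gives no figure for the ADA table. The event formula in SAP Appendix 1 gives [(1.960 + 1.282)/ln 0.4]² × 16/3 = 66.7, rounded up to the stated 67.

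**3. Assumptions not in the documents.** A fraction p = 5% or 15% of subjects would seroconvert by Day 197, independently of attacks (no true ADA effect). Timing is evenly spread over the RCP, all by Day 29, or all after Day 85. Baseline positives are 0% or 5%. No dropout.

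**4. Attack-free probability.** S(d) = 0.8·exp(−0.6d/365) + 0.2·exp(−0.4d/365), so S(29) = 0.9565, S(57) = 0.9163, S(85) = 0.8779 and S(197) = 0.7399. The overall attack risk is 1 − 0.7399 = 26.0%.

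**5. Rule as written, even timing, no baseline positives.** The Day 197 sample is drawn at the Day 197 visit, not before it, so only Days 29 and 85 can make an attack-free subject newly positive.

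- P(newly positive) = p × (29 × 0.9565 + 56 × 0.8779)/197 = p × 76.90/197 = 0.390p.
- Attack risk if positive = 1 − (85 × 0.7399)/76.90 = 1 − 62.89/76.90 = 18.2%.
- Attack risk if negative, p = 5%: (0.2601 − 0.0195 × 0.182)/(1 − 0.0195) = 26.2%. Ratio 0.70.
- At p = 15%: 18.2% against 26.5%. Ratio 0.69.

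**6. Other settings, still with no true ADA effect.** If all seroconversion is by Day 29, the risk in positives is 1 − 0.7399/0.9565 = 22.6%. A baseline fraction b is pooled in as b × 26.0% with no immortal time.

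| Setting | Risk ratio, p = 5% | Risk ratio, p = 15% |
|---|---|---|
| Rule as written, even timing | 0.70 | 0.69 |
| Rule as written, all by Day 29 | 0.87 | 0.85 |
| Rule as written, even timing, 5% baseline positive | 0.91 | 0.83 |
| Rule as written, all by Day 29, 5% baseline positive | 0.93 | 0.89 |
| Rule as written, all after Day 85, 5% baseline positive | 1.0 | 1.0 |
| Day 197 sample also counted, even timing, no baseline positives | 0.33 | 0.31 |

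For the last row, the risk in positives is 1 − (197 × 0.7399)/(76.90 + 112 × 0.7399) = 1 − 145.8/159.8 = 8.8%, against 26.7% in negatives at p = 5%.

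**7. Cumulative attacks tabulated visit by visit.** By Day 57 (even timing, p = 5%, no baseline positives), the risk in positives is 1 − 0.9163/0.9565 = 4.2%, against 8.4% in negatives. Repeating the cumulative count at each visit does not remove the bias.

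**8. The repair.** Among subjects attack-free at the start of each interval, the null risk does not depend on ADA status: 1 − 0.8779/0.9565 = 8.2% for Days 29 to 85, and 1 − 0.7399/0.8779 = 15.7% for Days 85 to 197. In a simulation of these settings, attacks per person-year by time-updated status gave null rate ratios of 0.995 to 1.005.

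**9. Size in subjects.** Under step 5, 189 × 0.0195 = 3.7 to 189 × 0.0586 = 11.1 MEDI-551 subjects would be newly positive. Expected attacks among them are 0.7 to 2.0, against 1.0 to 2.9 at the unbiased 26.0%: a shortfall of about 0.3 to 0.9 of an attack.

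**The case against.** The best defence is that the SAP already avoids the crude comparison. It does not use ever-positive status: only earlier samples count, and status is carried forward in time. That is close to the exposure definition a time-dependent analysis would use, and it keeps ADA first found after an attack from being counted. Moreover, if each time point were read as new attacks among subjects still at risk, the comparison would be unbiased. This stands as far as it goes. The earlier-sample rule shrinks the bias (about 0.7 rather than 0.3) but does not remove it, and the SAP never states the at-risk reading. Its named statistic, a percentage of subjects over the RCP, points the other way.

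It is also true that baseline positives carry no immortal time and dilute the effect, that the separate baseline-ADA bullet is unaffected, and that sampling noise in so few subjects would exceed the shift in step 9. Small numbers make the table imprecise, but they do not make it unbiased.

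A reader might infer that ADA-positive subjects would seem to have a third of the attack risk. That needs the Day 197 sample to count, which the stated rule excludes; for an attack-free subject the last qualifying sample is Day 85. Nor does the rule always enrich the positive group for non-attackers: with 5% baseline positives and only late seroconversion, the ratio is about 1.0.

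**Conclusion.** The concern holds as a minor point. Read as a whole-RCP percentage, the planned table is biased toward ADA looking harmless or protective. Under the rule as written and no true effect, the risk ratio is about 0.7 with evenly spread seroconversion, about 0.86 with early seroconversion, and about 0.83 to 1.0 with 5% baseline positives. These figures rest on the SAP's design hazards, no dropout, and assumed ADA incidence, timing and baseline prevalence; the direction does not depend on the exact values, but the size does.

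The documents do not support extending this to the trial's efficacy conclusions. The ADA tables are descriptive and lie outside the hypotheses covered by the Type I error procedure in SAP Section 4 and Appendix 3, so the primary and key secondary results are unaffected.

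**What to change.** In SAP 3.8, within the MEDI-551 arm, replace the percentage by cumulative status with attacks per person-year by time-updated ADA status, taking the status at the last sample before each time so that a subject contributes time first as negative and then, if applicable, as positive. A simpler alternative is a landmark table: among subjects still attack-free at Day 29, attacks after Day 29 by ADA status at Day 29. In either case state the at-risk denominator, and say explicitly that samples drawn at the attack or Day 197 visit do not count toward status for that visit. Keep the baseline-ADA table as it is. Add ADA as a time-dependent Cox covariate only if there are enough attacks in ADA-positive subjects to support it.

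No new data are needed. The cost is a few lines of SAP text and minor programming. The downside is that the estimates will be imprecise, because few subjects are likely to be positive.
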